PVI	:	Pulmonary Vein Isolation
R&D	:	Research and Development
SAE	:	Serious Adverse Event
s	:	Seconds
SSA	:	Site Specific Assessment
TOE	:	Trans-Oesophageal Echocardiogram
TSC	:	Trial Steering Committee
µmol	:	Micromole

AVATAR-AF Protocol Summary

SPONSOR	Imperial College London Academic Health Science Centre
PROTOCOL TITLE	Ablation Verses Anti-arrhythmic Therapy for Reducing All Hospital Episodes from Recurrent Atrial Fibrillation (AVATAR-AF)
STUDY HYPOTHESIS	A streamlined AF ablation procedure done without PV mapping as a daycare is more effective than anti-arrhythmic drugs at reducing all hospital episodes for recurrent atrial fibrillation.
STUDY DESIGN	Multicentre, randomised clinical trial
TREATMENT REGIMEN	Arm 1-AVATAR-AF Ablation Protocol Arm 2-Anti-arrhythmic therapy Arm 3-Conventional AF Ablation
MAIN INCLUSION CRITERIA	
1. Documented paroxysmal atrial fibrillation2. Modification or initiation of anti-arrhythmic agent required for symptom control3. Males or females eighteen (18) to eighty (80) years of age.4. Suitable candidate for catheter ablation5. Signed informed consent
MAIN EXCLUSION CRITERIA	
1. Contraindication to catheter ablation2. No carer to enable daycare discharge3. Arrhythmias other than AF documented unless they have had curative ablation (eg. for atrial flutter)§ – Please see page 13 for more details.4. No documentation of sinus rhythm within 3 months5. Valvular or other heart disease needing regular follow up6. EF <45% or moderate/severe LV dysfunction (determined by Echocardiogram in the last 6mths)7. Active gastrointestinal disease precluding anticoagulation or trans-oesophageal echocardiogram8. Renal failure with creatinine >200 µmol/L or on dialysis9. Active fever or infection10. Life expectancy shorter than the trial11. Allergy to contrast12. Severe cerebrovascular disease precluding daycare discharge13. Bleeding or clotting disorders or inability to receive heparin14. Uncontrolled diabetes (HbA1c ≥73 mmol/mol or HbA1c ≤64 mmol/mol and Fasting Blood Glucose ≥9.2 mmol/L (shown in the last six months without evidence of being brought under control)15. Serum Potassium [K⁺] <3.5 mmol/L or >5.0 mmol/L (shown in the last six months without evidence of being brought under control)16. Malignancy needing surgery, chemotherapy or radiotherapy17. Pregnancy or women of child-bearing potential not using a highly effective method of contraception18. Must not have previous (4 weeks prior to screening) or current participation in another clinical trial with an investigational drug or investigational device19. Unable to give informed consent

	20. Uncontrolled thyroid disease defined as abnormal thyroid function tests causing cardiac manifestations within the last 6mths 21. Unable to attend follow-up visits
NUMBER OF PATIENTS	321 patients, 1:1:1 randomisation
DURATION OF STUDY	1 year recruitment period/1 year follow-up for each patient
NUMBER OF SITES	13 United Kingdom sites
PRIMARY ENDPOINT	Time to any hospital episodes (Emergency Room or outpatient) related to treatment for atrial arrhythmia
SECONDARY ENDPOINTS	
 1. Time to Death or Stroke from any cause 2. Any complications caused by the procedure (pericardial effusion, bleeding >2 units, phrenic nerve palsy and other) or the anti-arrhythmic drug (GI disturbance, skin irritation and other) 3. All hospital episodes which result in a change in therapy for atrial arrhythmia

1 INTRODUCTION

1.1 Background

Atrial fibrillation (AF) is the most common clinical cardiac arrhythmias and pulmonary vein isolation (PVI) has been shown to be more effective than anti-arrhythmic agents for maintaining sinus rhythm.¹⁻⁴ These comparative studies have used stringent methods for judging success. The current 2012 HRS/EHRA/ECAS guidelines recommend assessing outcome by 'any detectable AF' which is defined as 30seconds of sustained AF on a 24hour holter monitor or event recorder.⁵ The previous 2007 guidelines, on which most current practice is based also indicated that Holter monitoring should be performed every 6months for 2years. These outcome measures are effective for determining the efficacy of a technology but have limited use for decision making in patients. A one minute episode on a 24hr tape at 12 months after an ablation in an asymptomatic patient may be deemed a 'failure' on scientific grounds but would not result in a repeat ablation or change in medication. There is a risk that trying to achieve 'perfect' outcomes may lead to procedures that are more complicated than is necessary to meet the patient's needs. Furthermore, patients with effective symptom control are expected to attend for hospital review and investigation, with the associated inconvenience and resource consumption without any prospect of a change in management strategy. There is some evidence that pursuing such a strategy may improve the stroke risk in an asymptomatic patient, but this has not been incorporated into any guidelines.^{6,7} Multiple Holter recordings demonstrating sinus rhythm are reassuring but in patients with a high CHADSVASC score, the absolute reduction in risk and long term recurrence is not known. We would suggest that the main value of Holter recording is to diagnose the cause of ongoing palpitations following ablation as these may not be AF.

Therefore, we would propose that the definition of success in AF ablation and its implication needs re-evaluation. One level of success would be to eliminate stroke risk. This may need frequent monitoring and prevention of all episodes of AF both symptomatic and asymptomatic. Such an approach may need aggressive ablation endpoints with increased procedural and long term follow-up costs.⁸ This may be justified by the number of strokes prevented. Studies addressing such endpoints would need several thousand patients, similar to RELY, ROCKET-AF and ARISTOTLE, which is probably beyond the scope of interventional studies at present.⁹ Another level of defining success would be according to symptom control, but due to the lack of objectivity in symptom status, it has not been a popular endpoint for studies. Quality of life questionnaires have been used but most clinicians find these cumbersome to use and the data analysis difficult to understand.¹⁰ As an alternative we would propose that attending hospital appointments and investigations both electively or as an emergency are objective and measurable events. Hospitalisation for inpatient treatment is a well-established endpoint and adding routine outpatient appointments is a minimal change but is more relevant to this type of symptom monitoring. Following post-operative checks after an AF ablation, symptom control that is good enough to not need regular review could be used a 'success' measure. 'If successful, you will not need to attend hospital' is also a tangible outcome measure for the patient unlike the current outcome target of 'any detectable AF which requires the physician to clarify and then add the caveat of the limitations of the detection method and that stroke risk remains unknown despite this seemingly conclusive outcome. Furthermore, using hospital episodes aligns the results of the procedure with those used by healthcare commissioners.

This re-evaluation of the objectives of AF ablation, also raises the question of which components of an AF ablation procedure are needed to deliver the effective symptom control rather than prevent any detectable AF. Originally, pulmonary vein (PV) ectopic foci were shown to trigger AF and a technique for identifying and ablating these ectopic foci was proposed as a potential treatment for AF. The unpredictability of ectopy and the high incidence of PV stenosis, led to this approach being abandoned in favour of ostial segmental pulmonary vein isolation (PVI) guided by circular PV mapping catheter on the basis that >90% of ectopy originated from the PV. Subsequently it was shown that circumferential antral ablation (CPVA) with acute isolation proven by PV mapping and entrance block was superior to segmental ostial ablation or ablation without PV mapping. Most current approaches are based on this data and produces a consistent and reproducible success rate of around 50-70% for paroxysmal AF.⁵ However,

the mechanism for success is uncertain as a significant proportion of ablated veins will electrically reconnect even in patients without AF recurrence.¹¹ It has been assumed that improving the durability of PV isolation by altering energy type and reducing the need for operator skill would be the path to better results and has included balloon ablation catheters such as the cryoballoon and laser balloon, robotic technologies and multipolar circumferential catheters that can map and ablate. However, there has been no discernible improvement with any of these approaches (though the cost per procedure has increased). We believe that this is because all these technologies use PV isolation as an endpoint and this is the outcome that can be expected using this endpoint.¹²⁻¹⁴ The attempts to demonstrate the benefits of these new technologies revealed some intriguing data, particularly the finding that ablation 'quality' in the antral region (by using steerable sheaths or simply additional lesions) has a better association with clinical outcomes than pulmonary vein isolation in multivariate analysis.^{15,16} This may be related to effect on the local autonomic innervation, but raises the question of the necessity of demonstrating pulmonary vein isolation during ablations using current ablation modalities.¹⁷ The need for an aggressive approach with electrical isolation of all veins has not been tested against symptom-based outcome measures such as the requirement for further hospital intervention.

Such a proposal may be controversial but its justification rests on whether symptom control or stroke prevention is the goal of AF ablation. Currently all guidelines indicate that symptoms are the only indication and yet 'any detectable AF' is used to assess procedures and it has become a 'sacred cow' that is rarely challenged.^{3,4,12-14} Cost-effectiveness studies on paroxysmal AF ablation, which have excluded any putative stroke or mortality benefits suggest incremental cost-effectiveness ratio of ablation versus medical therapy was \$51 431 per quality-adjusted life-year.¹⁸ This is still a considerable increase particularly as population studies suggest that the burden of AF is increasing with the aging population. Changing the definition of a successful ablation to the prospect of avoiding hospital episodes may enable the reduction of absolute costs of the procedure which would have a significantly beneficial effect on the cost effectiveness calculations. Review of our internal data suggests using the Advance™ Cryoballoon (Medtronic,Minneapolis) produces PV isolation >80% of veins without the need for additional ablation which requires PV mapping catheters. If the procedure is done without PV mapping, there are multiple cost savings PV mapping catheter, EP recording equipment and specialist staff. This would also shorten the procedure and may enable most patients to be completed as a day case which would be a cost saving through reduced bed occupancy. One series has suggested that nearly 90% of patient can already be discharged safely as a daycare.¹⁹ Our annual audits would support this view in that most complications (pericardial effusion, femoral bleeding, urinary retention, phrenic nerve injury) occur within three hours of the end of the procedure. The rest do not present during the overnight stay (atrio-oesophageal fistula, pulmonary vein stenosis, delayed tamponade). Simply changing the definition of success may enable all of these cost-savings to be made without compromising outcome to the patient.

In summary, developments in paroxysmal AF ablation have been monitored against the definition of any detected 30seconds of AF, which is not necessarily measure of symptom control. Hospital episodes are an objective and well established endpoint throughout the healthcare system and are more reflective of the patient's expectations. The increasing population burden of AF will need more cost effective approaches to treatment of symptoms. It is not known whether current approaches to antral pulmonary vein ablation still necessitates pulmonary vein mapping, which is a major source of to cost and complexity.

The proposed study is based on the following observations:

- i) AF ablation is well established as the most effective method for preventing recurrence.
- ii) Current methods for AF ablation are costly and complex with only a small minority of the AF population having access to such procedure.
- iii) The Advance Cryoballoon is effective at producing antral PV ablation mapping.

iv) AF ablation has not been compared against anti-arrhythmic agents with the primary goal of controlling symptoms.

1.2 Research Hypothesis

A streamlined AF ablation procedure done without PV mapping as a daycare is more effective than anti-arrhythmic drugs at reducing all hospital episodes for recurrent AF.

2 STUDY OBJECTIVES

2.1 Primary Objective

To determine if antral AF ablation without electrophysiological confirmation of PV isolation is more effective than anti-arrhythmic agents at achieving freedom from hospital based treatment.

[figure not shown]
2.2 Secondary Objectives

To determine if antral AF ablation without electrophysiological confirmation of PV isolation performed as a daycare is less effective than the conventional approach.

3 STUDY DESIGN

AVATAR-AF is a multicentre, randomised controlled study comparing a streamlined AVATAR-protocol ablation procedure to anti-arrhythmic therapy in patients with documented paroxysmal AF who are considered to be failing current strategy for AF. A secondary control arm will also compare the AVATAR-protocol to conventional AF ablation. 321 patients who are on no prior anti-arrhythmic, 'pill-in-pocket' or taking regular anti-arrhythmics will be randomised in a 1:1:1 manner to a treatment strategy of either AVATAR-protocol ablation, anti-arrhythmic therapy or conventional AF ablation and followed-up for 1 year.

The study will be conducted in accordance with the protocol, Good Clinical Practice (GCP) and all applicable regulatory requirements.

4 Endpoints

4.1 Primary Endpoint

Time to all hospital episodes (Emergency Room or patient request for OPD) related to treatment for atrial arrhythmia.

4.2 Secondary Endpoints:

1. Time to death or stroke from any cause.
2. Any complications caused by the procedure (pericardial effusion, bleeding >2 units, phrenic nerve palsy and other) or the anti-arrhythmic drug (GI disturbance, skin irritation and other).
3. All hospital episodes which result in a change in therapy for atrial arrhythmia.

5 PATIENT RECRUITMENT

5.1 Patient Selection Procedures

Research staff will identify potential study patients against inclusion and exclusion criteria, before the Investigator determines their eligibility for participation. The Investigator will discuss the rationale for the study, study procedures, risks and benefits and all other issues mandated by the consent process. The potential participant will be offered an opportunity to participate in the study and written informed consent will be obtained if they agree. Study procedures and assessments will only be performed after written informed consent has been obtained.

At the screening visit, the patients general health will be assessed in a physical examination and recording of vital signs. The patient's medical and medication history will also be recorded.

A fasting blood sample will also be taken to exclude patients with uncontrolled diabetes or $[K^+]$ and serum creatinine outside acceptable safety ranges and the patient will be asked to complete a Quality of Life questionnaire (EQ5D) and an Atrial Fibrillation Effect on QualiTy of life (AFEQT) questionnaire. A blood test result within 6 months is acceptable. Any blood test result taken more than 6 months prior to randomisation will need to be repeated. A copy of the blood results must be filed in the patient notes. Any other routine clinical tests should be performed as per local practice.

Both the AVATAR protocol and conventional ablation procedures will be discussed with the patient and the anti-arrhythmic agent or the change in dose that would be selected as the next line of treatment would be agreed at this stage in preparation for potential anti-arrhythmic arm.

The informed consent process and all study assessments will be documented in the patient's medical notes and study case report forms.

5.2 Inclusion Criteria

To be eligible for the trial, subjects must meet all of the following criteria:

1. Documented paroxysmal atrial fibrillation
2. Modification or initiation of anti-arrhythmic agent required for symptom control
3. Males or females eighteen (18) to eighty (80) years of age
4. Suitable candidate for catheter ablation
5. Signed informed consent

5.3 Exclusion Criteria

Subjects with any of the following will be excluded from the study:

1. Contraindication to catheter ablation
2. No carer to enable daycare discharge
3. Documented Arrhythmias other than AF unless they have had curative ablation (eg. for atrial flutter)[§]
4. No documentation of sinus rhythm within 3 months
5. Valvular or coronary heart disease needing regular follow up
6. EF <45% or moderate/severe LV dysfunction(determined by Echocardiogram in the last 6 months)

7. Active gastrointestinal disease precluding anticoagulation or trans-oesophageal echocardiogram
8. Renal failure with creatinine $>200 \text{ }\mu\text{mol/L}$ or on dialysis
9. Active fever or infection
10. Life expectancy shorter than the trial
11. Allergy to contrast
12. Severe cerebrovascular disease
13. Bleeding or clotting disorders or inability to receive heparin
14. Uncontrolled diabetes (HbA1c $\geq 73 \text{ mmol/mol}$ or HbA1c $\leq 64 \text{ mmol/mol}$ and Fasting Blood Glucose $\geq 9.2 \text{ mmol/L}$) (shown in the last six months without evidence of being brought under control)*
15. Serum Potassium $[\text{K}^+] < 3.5 \text{ mmol/L}$ or $> 5.0 \text{ mmol/L}$ (shown in the last six months without evidence of being brought under control)
16. Malignancy needing surgery, chemotherapy or radiotherapy
17. Pregnancy or women of child-bearing potential not using a highly effective method of contraception **
18. Must not have previous (4 weeks prior to screening) or current participation in another clinical trial with an investigational drug or investigational device
19. Unable to give informed consent
20. Uncontrolled thyroid disease defined as abnormal thyroid function tests causing cardiac manifestations within the last 6mths21. Unable to attend follow up visits

§ AVATAR-AF Guidance on Atrial Flutter

- (I) **12 lead ECG documentation of typical atrial flutter during screening**
 - *Patient should not be recruited to the AVATAR study and should undergo Cavo-Tricuspid Isthmus line(CTI) ablation.*
 - *If symptomatic atrial fibrillation is still present then the patient can be considered for AVATAR recruitment.*
- (II) **12 lead ECG documentation of typical atrial flutter after randomisation.**
 - *Patient should be suspended from the AVATAR study intervention and should undergo CTI ablation.*
 - *If symptomatic atrial fibrillation still present then the patient can be considered for AVATAR intervention.*
- (III) **Holter monitor – Atrial fibrillation + organised atrial activity suggestive of paroxysmal atrial flutter.**
 - *Can be recruited to AVATAR study, but cannot have CTI at first ablation.*
- (IV) **CTI dependent flutter (or any other arrhythmia) occurs during AF ablation procedure.**
 - *These patients should not be ablated during the first ablation procedure*
- (V) **Symptomatic atrial flutter picked up as an endpoint.**
 - Can progress to ablation as per physician discretion*

* A fasting blood glucose must have been done within the last 6mths confirming that blood glucose under control. If no blood test result available, a new fasting blood glucose sample will be taken from all consented potential participants at screening to exclude uncontrolled diabetes, defined as:

- HbA1c $\geq 73 \text{ mmol/mol}$ or
- HbA1c $\leq 64 \text{ mmol/mol}$ and Fasting Blood Glucose $\geq 9.2 \text{ mmol/L}$

** Women of child-bearing potential not using a highly effective method of contraception must undergo a pregnancy test. Acceptable methods of contraception include the following:

- Barrier type devices (e.g. female condom, diaphragm and contraceptive sponge) used ONLY in combination with a spermicide.
- Intra-uterine devices.
- Oral contraceptive agents started at least 90 days before start of study.
- Depo-Provera (medroxyprogesterone acetate).
- Levonorgestrel implants.
- Naturally or surgically sterile (amenorrhoeic for at least 1 year and no record of child birth for naturally sterile persons).
- Male partner is sterile and is the only sexual partner

Women not of child-bearing potential and eligible for the trial will have been hysterectomised, sterilised or be post-menopausal (ie. at least one year since their last period).

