5.4 Randomisation Procedures

Eligible patients who have given written, informed consent and who meet all the inclusion criteria and no exclusion criteria will undergo 1:1:1 randomisation to an un-blinded treatment of either AVATAR-protocol AF Ablation, medical anti-arrhythmic therapy or conventional AF ablation. Randomisation will be performed electronically using the InForm electronic data capture system and will be stratified by site.

From the date of randomisation, the 1st Intervention date (ablation or anti-arrhythmic medication change) must occur 28 days ± 7days after this, therefore an ablation procedure date will be identified according to local EP catheter lab availability for each consenting, eligible patient and randomisation of the patient will then be scheduled for 28 days ± 7days from this available date.

The patient may be withdrawn from any AF ablation treatment by the Investigator if any safety concerns arise during the period between randomisation and the ablation which make the patient an unsuitable candidate for the procedure. The patient will then be withdrawn from the study.

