** Women of child-bearing potential not using a highly effective method of contraception must undergo a pregnancy test. Acceptable methods of contraception include the following:

- Barrier type devices (e.g. female condom, diaphragm and contraceptive sponge) used ONLY in combination with a spermicide.
- Intra-uterine devices.
- Oral contraceptive agents started at least 90 days before start of study.
- Depo-Provera (medroxyprogesterone acetate).
- Levonorgestrel implants.
- Naturally or surgically sterile (amenorrheic for at least 1 year and no record of child birth for naturally sterile persons).
- Male partner is sterile and is the only sexual partner

At the screening visit, the patient will be examined to ensure that none of the exclusion criteria are met. Their general health will be assessed in a physical examination and recording of vital signs. The patient's medical and medication history will also be recorded. A fasting blood sample will also be taken to exclude patients with uncontrolled diabetes or [K+] and serum creatinine outside acceptable safety. A blood test result within 6 months is acceptable. Any blood test result taken more than 6 months prior to randomisation will need to be repeated. A copy of the blood results must be filed in the patient notes. Any other routine clinical tests should be performed as per local practice.

If the patient does not meet any of the exclusion criteria and no additional complications are encountered during the screening process then once written, informed consent has been received the patient is eligible for randomisation.

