8.7. Tables to Present

Table 1.1: Subject Disposition

	Site A	Site B	...	Total
Screened				
Randomised				
Treatment A				
Treatment B				
Treatment C				
Withdrawn				
Reason for Withdrawal				
Completed				

Table 2.1: Listing of protocol deviations

Treatment	Subject	Site	Type	Start Date	End Date

Table 2.2: Number of protocol deviations by centre and category

Type of Deviation	Site A	Site B	...	Total
Patient was incorrectly included in the trial (did not meet all the inclusion and exclusion criteria)				
:				
Patient pregnancy				
Other				
Total				

Table 3.1: Baseline characteristics

Variable	Statistics	AVATAR-AF Ablation	Anti-arrhythmic therapy	Conventional AF Ablation
Age (y)	N Mean SD Min Median Max			
Race (n (%))	xxxxxx xxxxxx			
Ethnicity (n (%))	xxxxxx xxxxxx			
Gender (n (%))	Female Male			
Height (cm)	N Mean SD Min Median Max			
Weight (kg)	N Mean SD Min Median Max			
Pulse (bpm)	N Mean SD Min Median Max			
Systolic BP	N Mean			

	SD	
	Min	
	Median	
	Max	
Diastolic BP	N	
	Mean	
	SD	
	Min	
	Median	
	Max	
QoL Score	N	
	Mean	
	SD	
	Min	
	Median	
	Max	
QoL Score (n (%))	<40	
	...	
	90-99	
	100+	
Chadsvasc Score (n (%))	0	
	1	
	..	
	6	
AFEQT Score	N	
	Mean	
	SD	
	Min	
	Median	
	Max	
AFEQT Score (n (%))	0-19	
	...	
	80-100	

Anti-Arrhythmics Taken (n (%))	Amiodarone	
	...	
	Propafenone	
Beta Blockers Taken (n (%))	xxxxx	
Calc. Ch. Blocker Taken (n (%))	xxxxx	
Record of Anti-Coag Pre-Procedure (n (%))	Yes – Bridging	
	Yes – Continuous	
	No	
Expectation of Anti-Coag Post-Procedure (n (%))	Yes	
	No	
Subjects displaying evidence of Paroxysmal Atrial Fibrillation (n (%))	Yes	
	No	
ECG Rhythm (n (%))	Sinus	
	SVT	
	...	
	Q-Waves	
Ejection Fraction (%)	N	
	Mean	
	SD	
	Min	
	Median	
	Max	
Pericardial Effusion (n (%))	Yes	
	No	
Presence of Thrombus (n (%))	Yes	
	No	

***Table Note: To include the following variables - Age, race, ethnicity, gender, height, weight, pulse rate, Systolic BP, Diastolic BP, QoL Score, AFEQT Score, CHADSVASC Score, Heart Medications Taken, Record of Anti-Coagulation pre-procedure, Anti-Coagulation requirements post-procedure 24hr Holter, ECG, Echocardiology.**

PRIMARY ENDPOINT

Table 4.1: Listing of all hospital episodes (Emergency Room or patient request for OPD) related to treatment for atrial arrhythmia.

Treatment	Subj.	Date of Visit	Discharge Protocol?	Reason for Adjudication	Outcome	Endpoint?	Time to Event

Table 4.2: Log-rank test investigating occurrence of AF related hospital visits*

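### The mandated pregnancy test covers only women whom exclusion 17 already bars, and no test is specified for the women of child-bearing potential who can be randomised

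*Protocol*

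**What the plan says.** - **The exclusion.** Protocol 5.3, criterion 17, excludes "Pregnancy or women of child-bearing potential not using a highly effective method of contraception". The Protocol Summary and SAP 5.4 list the same criterion.
- **The test.** The double-asterisk footnote to that criterion says "Women of child-bearing potential not using a highly effective method of contraception must undergo a pregnancy test", and then lists acceptable methods of contraception. SAP 5.4 carries the same sentence.
- **The randomisation rule.** Under Protocol 5.4, repeated in SAP 5.7, it is consenting patients "who meet all the inclusion criteria and no exclusion criteria will undergo 1:1:1 randomisation". No exception for a negative pregnancy test is written there or elsewhere.
- **Screening procedures.** Protocol 5.1 gives the purpose of the blood sample: "A fasting blood sample will also be taken to exclude patients with uncontrolled diabetes or" potassium or creatinine outside the safety range. It adds: "Any other routine clinical tests should be performed as per local practice". SAP 5.4 says that at screening "the patient will be examined to ensure that none of the exclusion criteria are met".
- **Schedule.** The visit tables in Protocol section 9 and SAP 5.6 have rows for eligibility, medical history and a fasting blood sample at Screening. Neither has a row for a pregnancy test.
- **Reporting.** SAP 8.7, Table 2.2, includes "Patient pregnancy" among the protocol-deviation categories.

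**The concern.** A test attached to an exclusion criterion should help to decide who is eligible. Here it is attached to women whose eligibility is already settled by their contraceptive status. It is not attached to the women for whom pregnancy is the open question. A site that follows the text exactly would test women it cannot enrol, and would have no instruction to test the women of child-bearing potential it can enrol.

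The stake is patient safety and uniform eligibility across the 13 sites, not the statistical inference. After randomisation, patients wait and then have either a catheter procedure with pulmonary venography or a change of anti-arrhythmic drug. The plan names no step that would check for pregnancy in enrolled women before either one.

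**Working it through.** The plan gives no figure to reproduce. The check sets criterion 17, its footnote and the randomisation rule side by side. It assumes that a method on the footnote's list counts as highly effective, since the documents define the term in no other way.

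| Women of child-bearing potential | Barred by criterion 17? | Test required by footnote? | Can be randomised? |
|---|---|---|---|
| No highly effective method | Yes, by the contraception limb | Yes | No, whatever the result |
| Listed method, not pregnant | No | No | Yes |
| Listed method, pregnant | Yes, by the pregnancy limb | No | No, but no named test identifies her |

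**Step 1: the footnote as an added check.** The women who must be tested are in the first row, and the women who can be randomised are in the second. The two groups do not overlap. The only rows in which a test could change a decision are the second and third, and no test is required in either.

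**Step 2: the footnote as an exception.** Suppose a negative test admits a woman from the first row. The test then has a purpose, but criterion 17 no longer excludes the group it names, and the rule in Protocol 5.4 and SAP 5.7 is broken. Women using a listed method still have no test. The gap for them is therefore present on both readings.

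**Step 3: other steps that might fill the gap.**
- The screening blood sample is for diabetes, potassium and creatinine.
- The schedules tick eligibility at Screening only.
- Other exclusions have a named measurement: echocardiography for ejection fraction, HbA1c and fasting glucose for diabetes, serum potassium and serum creatinine. Pregnancy has a named test too, but for a different group from the one that can enter.

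**Step 4: the wait.** 1st Intervention falls 28 ± 7 days after randomisation, that is 28 − 7 = 21 to 28 + 7 = 35 days. No repeat eligibility check is scheduled in that interval. Protocol 5.4 lets the investigator withdraw a patient from ablation if a safety concern arises in the wait. That clause provides no means of detecting pregnancy and does not mention the drug arm.

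**The case against.** The strongest reply is that a test which is not mandated is not thereby forbidden. Protocol 5.1 leaves other routine tests to local practice, the investigator determines eligibility, medical history is taken, and SAP 5.4 has every exclusion checked at screening. The withdrawal clause in Protocol 5.4 gives some protection during the wait in the ablation arms. All of this stands.

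A reader might infer that eligible women are never tested, that the pregnancy exclusion cannot be enforced, or that it is applied by self-report alone. The documents support none of these, because they do not show what sites do. Nor does Table 2.2 show that a pregnancy would come to light only after treatment. It is an empty table shell and says nothing about when or how a pregnancy is found.

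It can also be said that reading the footnote as an exception is weak, because the randomisation rule leaves no room for one. That is fair, and it makes opposite decisions at different sites a possibility rather than an expectation. Finally, whether women on a listed method need a mandated test is partly a clinical design choice. That too is fair, but it does not explain a test aimed only at women who cannot enter.

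**Conclusion.** The point holds in a limited form. As written, the mandated test applies only to women already excluded, or else the footnote contradicts its own criterion. The SAP copies the sentence and so does not resolve it. For women of child-bearing potential who can be randomised, the pregnancy exclusion rests on history, the general eligibility check and local practice that the plan does not describe.

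The documents do not give the number of such women among the 321 patients. It is presumably small, but that is an assumption. Any count would be of women for whom no test is specified, not of undetected pregnancies, which would be some fraction of it. There is no effect on alpha, power or sample size. The conclusion rests on the text alone and on treating a listed contraceptive method as meeting the highly effective standard.

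**What to change.** Reconcile criterion 17, its footnote and the visit schedule in the Protocol (5.3 and section 9) and the SAP (5.4 and 5.6), so that:

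1. the verification step applies to the women who can be enrolled;
2. the status of women not using highly effective contraception can be read in only one way;
3. the text states how and when the pregnancy exclusion is verified, taking account of the 21 to 35 days between randomisation and 1st Intervention.

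The sponsor should choose the clinical rule, including whether a test is kept and at which visits. This review does not propose one.

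The cost is about one sentence in each document. If a test is kept, it adds one schedule row and a simple test in a subgroup whose size the documents do not give. No statistical analysis needs to change.
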